5.3. ACCOUNTABILITY OF THE STUDY PRODUCT

Upon receipt, the study staff designated by the Investigator will inventory the clinical study products, and complete and sign the Receipt of Study Product documentation. A copy of the form will be maintained in the Investigator's records and the original will be provided to Lexitas.

The designated study staff must keep a complete and accurate accounting of all Study Product used via a Dispensing Log. In no case will the Study Product be used in any unauthorized situation.

At Visits 3, 4, 5 and 6, patients will return the used or unused study boxes/vials to the clinic in the original carton.

All Study Product returned by patients should be inventoried same day of return. Inventory will take place at Visits 3, 4, 5 and 6. These records will be made available to the study monitor for the purpose of accounting for all study products. The study monitor will account for all Study Products. The investigator will maintain all used and unused vials after inventory for the duration of the clinical trial. Upon completion of the trial all used and unused vials will be packaged for return to Dompé once the study monitor has concluded no data from patient inventory reconciliation is missing. Once the study is concluded and all records are reviewed for accuracy the CRO will give the PI permission to package and return all vials to Dompé. Return instructions will be provided to investigators.

It is the Investigator's responsibility to ensure the reconciliation of study medications at the conclusion of the study. Any discrepancies and/or deficiencies in study drug accountability must be recorded along with an explanation in the appropriate accountability log.

Study Product which has been dispensed to a patient and returned unused will not be re-dispensed to a different patient.

Unused Study Product must not be discarded or used for any purpose other than the present study. Any remaining Study Product at the end of the trial will be disposed of as determined by Dompé.

5.3.1. Prior and concomitant medications

As a general rule, no ophthalmic medication other than Study Product and concomitant Study Product (Systane[®] -artificial tears provided by Sponsor) will be given to the patient from the screening day until all the final study evaluations have been completed. Systane[®], provided by the Sponsor, may be used *during screening and the follow up only*.

All medications (including over-the-counter drugs, systemic medications, herbal products, vitamins, and antacids) should be documented at screening and also taken within 14 days of study treatment Visit 2 and throughout the study will be clearly documented on the Concomitant Medications eCRF page.

Medication entries should be specific to product name (if a combination drug product) and spelled correctly. The dose, unit, frequency, route of administration, start date, discontinuation date, and indication should also be recorded. For medications administered only one time, the frequency column may reflect "once."

D Dompo	
Table 3 Medications and Procedures	Minimum Washout Period Prior to Treatment (Visit 2)
Have had incisional ocular surface surgery (e.g., LASIK, refractive, pterygium removal).	90 days
Ocular surgery (including eyelid surgery or cataract surgery)	90 days
Botox (botulinum toxin) injections in the study eye.	60 days
Any Investigational Product for NK	60 days
Any Investigational Product applied to the ocular surface if per the investigators discretion the investigational product does not have residual effects on the ocular surface that can confound the data	14 days
Topical ocular or systemic antibiotics for the treatment of an ocular condition	14 days
Topical cyclosporine (all doses and formulations)	14 days
Lifitegrast	14 days
Glaucoma topical medications (Use of Diamox orally during the study is acceptable)-Investigator should ensure stable IOP before/by Visit 2	14 days
Topical ocular corticosteroids, ocular non-steroidal anti- inflammatory drugs (NSAIDs), and topical dermatologic corticosteroids on the face within 14 days prior to Visit 2 and during study participation	14 days
Topical ocular antihistamine and/or mast cell stabilizers within 14 days prior to Visit 2. Have used topical ocular vasoconstrictors for the purpose of eye whitening within 14 days prior to Visit 2 (phenylephrine used to dilate the eyes is allowed).	14 days
Treatments for blepharitis MGD including but not limited to thermal pulsation (Lipiflow), debridement of lid margin (BlephEx), thermal application (MeiBoFlo, Tear Care), meibomian gland probing or doxycycline.	14 days
All topical ophthalmic gels, ointments or drops that can induce corneal toxicity (diagnostic medications used for clinical testing/evaluations are acceptable).	14 days
Enrollment of patients previously treated with amniotic membrane transplantation is allowed two weeks after the membrane has fully disappeared within the area with removal of any sutures or two weeks from removal of the Prokera ring before study treatment visit (Visit 2).	14 days

6. STUDY PROCEDURE AND ASSESSMENTS

For the detailed description of all the clinical examinations listed below refer to the Manual of Procedures (MOP). See the Schedule of Evaluations in Section 2.0 for the list of procedures by visit in the recommended order. The descriptions of the procedures to be performed at each visit are provided below. If possible, the same investigator should perform the assessments for one subject.

6.1. STUDY VISITS AND EXAMINATIONS AND TREATMENT VISITS

6.1.1. Visit 1 (Day -14): SCREENING

Site staff will conduct the following screening assessments in the order outlined below. (Note: Procedures that are not required to be conducted in a specific order will be noted with an *)

- 1. Informed Consent/HIPAA: Explain the purpose and nature of the study, and have the subject or legally authorized representative read, sign, and date the IRB approved informed consent document. Provide a photocopy of the signed document to the subject and place the original signed document in the subject chart.
- 2. *Demographics, Ocular and Medical History, Previous and Concomitant Ocular and Systemic Medications and Conditions: Document demographic information and medical history, including herbal therapies, vitamins, and all over the counter as well as prescription topical and systemic medications. Document etiology of NK and all concomitant ocular diseases and systemic conditions. Patients IOP should be measured at screening and if conversion to oral Diamox is initiated, patient should be deemed to have a stable IOP by Visit 2.
- **3.** *Pregnancy Test: Perform a urine pregnancy test on any female of childbearing potential and record the results. If a pregnancy test is not required, indicate as not applicable in the eCRF.
- 4. *Adverse Events: Begin monitoring of AE's.
- **5. Ophthalmic Examinations:** The following examination/procedures will be performed on BOTH EYES and in order unless otherwise specified. (The grading scale and detailed description of the examinations/procedures are described in the MOP):
 - a. Best-Corrected Distance Visual Acuity (BCDVA) Vision must be measured at each visit using ETDRS visual acuity chart at 4 meters (13 feet). BCDVA testing should precede the administration of any eye drops to dilate or anesthetize the eye, or any examination requiring contact with the eye. If vision is corrected, the same correction should be used throughout the BCDVA testing.
 - b. External Ocular Examination Assess the motility of the extraocular muscles and the appearance and function of the eyelids before the instillation of any dilating or anesthetic eye drops.

- c. Slit Lamp Examination (SLE): SLE will assess eyelids, lashes, conjunctiva, cornea, lens, iris, and anterior chamber. The slit lamp examination must be performed before the instillation of any dilating or anesthetic eye drops or the fluorescein agent.
- d. Corneal Photo Without Fluorescein: Photos of the cornea of both eyes (Visit 1) and the treated eye(s) (Visit 2, Visit 4, Visit 6, and Visit 7) will be taken after slit lamp examination and before the instillation of fluorescein agent by a slit lamp camera focusing on the epithelial defect and using white, diffuse (homogenous) frontal illumination.
- e. Instill Fluorescein
- f. Corneal Fluorescein Staining: Following the instillation of fluorescein in the qualifying eye(s) grade (density) of the SPK will be determined using the NEI (National Eye Institute [NEI]/Industry Workshop 0-15) scale.
- g. Corneal Photo with Fluorescein: As soon as possible after completing the Corneal Fluorescein Staining, a corneal photo of both eyes (Visit 1) and the treated eye(s) (Visit 2, Visit 4, Visit 6, and Visit 7) using cobalt blue illumination will be taken to document the observed corneal findings.
- h. Corneal Sensitivity: Corneal Sensitivity will be measured using a Cochet Bonnet aesthesiometer before the instillation of any dilating or anesthetic eye drops. Corneal sensitivity will be assessed in the qualifying NEI zones of each eye. Nonqualifying zones (excluding superior) may be tested if the qualifying NEI zone does not meet the corneal sensitivity inclusion.
- i. IOP
- 6. Inclusion/Exclusion Criteria Screen the subject for protocol inclusion/exclusion criteria as per Sections 4.1 and 4.2.
- 7. **Dispense Systane Original**[®]: Instruct patient to use only as strictly needed and up to 4 times per day during screening period; additionally, instruct the patient to return Systane[®] bottle (s) at Visit 2
- 8. *Dispense Study dosing diary (for Systane use)
- 6.1.2. Visit 2 (Day 0 ± 2 days): BASELINE

Patients will enter the single-arm open-label phase of the study if they continue to meet eligibility criteria at Visit 2/Baseline.

1. **IDEEL** (**Impact of Dry Eye on Everyday Life**): This questionnaire will be assessed by the patient using a self-administered format. This questionnaire is designed to assess health-related

quality of life in patients with visual impairments by representing the patient perspective on the impact of vision problems on functioning.

- **2. EQ-5D-5L:** This self-administered questionnaire will be completed by the patient before any ophthalmic examination is performed at a given study visit. The EQ-5D is a standardized measure of health status developed by the EuroQol Group in order to provide a simple, generic measure of health for clinical and economic appraisal.
- 3. *Concomitant Ocular and Systemic Medications Update: Record any change from Screening/Visit 1 in concurrent ocular or non-ocular medications including information on all concomitant and previous medications used within the past 14 days before Visit 2.
- 4. *Record AE's
- **5.** *Pregnancy Test: Perform a urine pregnancy test on any female of childbearing potential and record the results. If a pregnancy test is not required, indicate as not applicable in the eCRF.
- **6. Ophthalmic Examinations:** following examination/procedures will be performed on BOTH EYES unless otherwise specified:
 - a. BCDVA
 - b. External Ocular Examination
 - c. Slit Lamp Examination
 - d. Corneal Photo Without Fluorescein
 - e. Instill Fluorescein
 - f. Tear Film Break-Up Time (TFBUT)
 - g. Corneal Fluorescein Staining: Using NEI scale (0 to 3 is used for each of the five areas per cornea).
 - h. Corneal Photo with Fluorescein
 - i. Wait 10 minutes before performing Schirmer Test
 - j. Corneal Sensitivity
 - k. Schirmer Test Without Anesthesia (Schirmer I)
 - l. IOP
 - m. Anterior Segment OCT (selected sites)

- n. Confocal microscopy (selected sites)
- 7. Inclusion/Exclusion: Patients must continue to meet the Screening/Enrollment Criteria. At the end of the Baseline Visit (Day 0), it will be determined if the subject qualifies for continued participation and treatment in the study.
- **8. Study Product Dispensing:** Eligible patients will be supplied with a biweekly kit of Study product sufficient for 2 weeks of treatment per visit.
- 9. *Dispense Daily Study Dosing Diary
- 10. Collect used/unused AT and collect/review AT dosing diary
- 11. *Instructions to Subject: Instruct the subject to initiate dosing the study eye or *bilaterally* (if applicable) the following day and to return to the clinic for Visit 3/Week 2 Visit in 2 weeks (14 days). Further instruct the subject to return to the clinic with the Daily Study Dosing Diary and all the empty used/unused daily kit of Study product in the original carton box. Also, remind subject that Systane®, nor any other topical ocular medications), are allowed during study product treatment period.
- 6.1.3. Visit 3 (Day 14/Week 2 2 days) STUDY PRODUCT PICK-UP VISIT
 - 1. *Concomitant Ocular and Systemic Medications Update
 - 2. *Record AE's
 - 3. *Collect Used/Unused Study Product, Daily Dosing Diary, and Inventory
 - **4.** *Study Product Dispensing: Patients will be supplied with a biweekly kit of Study product sufficient for 2 weeks of treatment.
 - 5. *Dispense Daily Study Dosing Diary
- 6.1.4. Visit 4 (Day 28/Week 4 -2 days): TREATMENT VISIT
 - 1. IDEEL
 - 2. EQ-5D-5L
 - 3. *Concomitant Ocular and Systemic Medications Update
 - 4. *Record AE's
 - **5. Ophthalmic Examinations:** The following examinations/procedures will be performed on BOTH EYES unless otherwise specified:
 - a. BCDVA

- b. External Ocular Examination
- c. Slit Lamp Examination
- d. Corneal Photo Without Fluorescein
- e. Instill Fluorescein
- f. TFBUT
- g. Corneal Fluorescein Staining
- h. Corneal Photo with Fluorescein
- i. Wait 10 minutes before performing Schirmer Test
- j. Corneal Sensitivity
- k. Schirmer Test Without Anesthesia (Schirmer I)
- 6. *Collect used Study product and Daily Study Dosing Diary
- 7. *Study Product Dispensing: Patients will be supplied with a new biweekly kit of Study product sufficient for 2 weeks of treatment.
- 8. *Dispense Daily Study Dosing Diary
- **9. Instructions to Patient:** Instruct the patient to return to the clinic for Visit 5/Week 6 Study product Pick-Up visit in two weeks. Further instruct the patient to return to the clinic with the Daily Study Dosing Diary and all the empty used/unused daily kit of Study Product in original carton box.
- 6.1.5. Visit 5 (Day 42/Week 6 2 days): STUDY PRODUCT PICK-UP VISIT
 - 1. * Concomitant Ocular and Systemic Medications Update
 - 2. *Record AE's
 - 3. *Collect Used/Unused Study Product, Daily Study Dosing Diary, and Inventory
 - **4.** *Study Product Dispensing: Patients will be supplied with a biweekly kits of Study product sufficient for 2 weeks of treatment.
 - 5. *Dispense Daily Study Dosing Diary
 - **6. *Instructions to Subject:** Instruct the patient to return to the clinic for Visit 6/Week 8 End of Treatment visit in two weeks. Further instruct the patient to return to the clinic with the Daily Study Dosing Diary and all the empty used/unused daily kit of Study Product in the original

carton. Patients should be instructed to try and complete therapy before last treatment appointment, so at time of end of treatment evaluation the patient should have completed the six times a day dosing on Day 56/Week 8 for Visit 6. This will require PIs and their staff to try and schedule the last visit at the end of the day, so the patient has sufficient time to complete 6 doses on the day of Visit 6.

- 6.1.6. Visit 6 (Day 56/Week 8 4 days): END OF TREATMENT OR PREMATURE DISCONTINUATION VISIT
 - 1. IDEEL
 - 2. EQ-5D-5L
 - 3. *Pregnancy Test for women of childbearing potential: Perform a urine pregnancy test and record the results
 - 4. *Concomitant Ocular and Systemic Medications Update
 - 5. *Record AE's
 - **6. Ophthalmic Examinations:** The following examination/procedures will be performed on BOTH EYES unless otherwise specified:
 - a. BCDVA
 - b. External Ocular Examination
 - c. Slit Lamp Examination
 - d. Corneal Photo Without Fluorescein
 - e. Instill Fluorescein
 - f. TFBUT
 - g. Corneal Fluorescein Staining
 - h. Corneal Photo with Fluorescein
 - i. Wait 10 minutes before performing Schirmer Test
 - j. Corneal Sensitivity
 - k. Schirmer Test Without Anesthesia (Schirmer I)
 - l. IOP
 - m. Anterior Segment OCT (selected sites)

- n. Confocal Microscopy (selected sites)
- 7. Collect used Study Product and Subject Dosing Diary
- 8. Dispense Daily Study Dosing Diary
- 9. Dispense Systane®
- 6.1.7. Visit 7 (Day 224/Week 32 ±7 days): FOLLOW-UP/FINAL STUDY VISIT
 - 1. IDEEL
 - 2. EQ-5D-5L
 - 3. *Concomitant Ocular and Systemic Medications Update
 - 4. *Record AE's
 - **5. Ophthalmic Examinations**. The following examination/procedures will be performed on BOTH EYES unless otherwise specified:
 - a. BCDVA
 - b. External Ocular Examination
 - c. Slit Lamp Examination
 - d. Corneal Photo Without Fluorescein
 - e. Instill Fluorescein
 - f. TFBUT
 - g. Corneal Fluorescein Staining
 - h. Corneal Photo with Fluorescein
 - i. Wait 10 minutes before performing Schirmer Test
 - j. Corneal Sensitivity
 - k. Schirmer Test Without Anesthesia (Schirmer I)
 - l. IOP
 - m. Anterior Segment OCT (selected sites)
 - n. Confocal Microscopy (selected sites)

- 6. *Collect Daily Study Dosing Diary
- 7. Patient will be discharged from the study

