2.1. BACKGROUND INFORMATION

Neurotrophic keratitis (NK), also known as neurotrophic keratopathy, is a rare degenerative corneal disease caused by an impairment of corneal nerve innervation leading to a decrease or absence in corneal sensation. The cornea is an avascular tissue that is provided with the richest innervation of all body tissues via the trigeminal nerve. Corneal hypoesthesia or anesthesia and decreased reflex tearing

resulting from impaired corneal innervation can lead to a corneal epitheliopathy with a subsequent breakdown of the corneal epithelium, leading to potential visual impairment. Abnormal corneal sensation and epithelial defects with a poor tendency for spontaneous healing are the primary clinical manifestations of NK, which increase the risk for corneal complications associated with vision loss such as a persistent epithelial defect (PED), ulceration, melting, perforation and infectious keratitis. Neurotrophic keratitis has been divided into three stages according to the Mackie classification scheme and treatment recommendations are based on the severity of the corneal involvement.^[1]

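### At Visits 2, 4, 6 and 7 the 10-minute wait is listed before aesthesiometry and no interval is set after it, so touch-evoked tearing can carry over into Schirmer I

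*Protocol*

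**What the plan says.** Protocol Sections 6.1.2, 6.1.4, 6.1.6 and 6.1.7 give the same run of ophthalmic steps at Visits 2, 4, 6 and 7: (h) corneal photograph with fluorescein, (i) "Wait 10 minutes before performing Schirmer Test", (j) corneal sensitivity, (k) Schirmer I without anesthesia.

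Section 6.1.1 says of the touch test: "Corneal Sensitivity will be measured using a Cochet Bonnet aesthesiometer before the instillation of any dilating or anesthetic eye drops". Neither the touch nor the strip is therefore preceded by anesthetic. The same section explains how to read the lists: "Procedures that are not required to be conducted in a specific order will be noted with an" asterisk. Steps (h) to (k) carry none.

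The Schedule of Evaluations, described in Section 6 as the "list of procedures by visit in the recommended order", also places corneal sensitivity directly before Schirmer and shows no wait. Section 6 leaves the detailed description of the examinations to the MOP.

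Schirmer change from baseline at Weeks 4 and 8 is an exploratory objective (Protocol Section 3.1) and an efficacy endpoint (Section 7.1.1). SAP Section 5.2 lists it as a secondary variable and adds Week 32. SAP Section 5.4 plans descriptive statistics and an asymptotic 95% confidence interval for the mean change.

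**The concern.** The wait keeps the Schirmer strip away from the fluorescein steps, but it does not keep it away from the corneal touch. Schirmer I without anesthesia includes reflex tearing, and a filament touching an unanesthetized cornea is a stimulus for such tearing.

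Keeping the same order at every visit does not guarantee that the effect cancels in the change from baseline. Protocol Section 2.1 names "Corneal hypoesthesia or anesthesia and decreased reflex tearing" together as results of impaired innervation. Entry requires sensitivity of 4 cm or less in the central zone (Section 4.1), and improved sensitivity is a secondary objective and an endpoint. The tearing response to the touch may thus be weak at baseline and stronger once sensation recovers.

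At stake is what a rise in Schirmer means. Section 2.2 lists corneal innervation and tear secretion as separate mechanisms. If part of the rise is carry-over from the sensitivity test, Schirmer is partly a second reading of sensation. In a single-arm study nothing can be subtracted to separate the two, and no planned analysis attempts it.

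**Working it through.** **1. The order.** The sequence photograph, wait, sensitivity, Schirmer is the same at all four visits. The Schedule of Evaluations agrees on sensitivity before Schirmer. Tear film break-up time, staining grade and both photographs all precede the touch; Schirmer I follows it.

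**2. Two readings of the wait.**
- The wait ends before sensitivity testing starts. Schirmer is then the next listed step after the touch, with no interval required.
- Sensitivity is tested during the wait. The gap from touch to strip can then be anything from 0 to 10 minutes, and may vary by site and visit.

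Neither reading sets a minimum gap after the touch.

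**3. Size.** The documents give no figure for touch-evoked wetting and no standard deviation (SD) for Schirmer, so there is no plan figure to reproduce. The following is an illustration on assumed inputs.

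- q = share of patients whose sensation has recovered, assumed 0.25 to 0.75.
- c = extra wetting from the touch in those patients relative to their own baseline, assumed 0 to 4 mm.
- Shift in mean change: B = q × c. Lowest: any q × 0 = 0 mm. Middle: 0.5 × 2 = 1.0 mm. Highest: 0.75 × 4 = 3.0 mm.
- SD of change, assumed 4, 6 or 8 mm; n = 35 (Protocol Section 9.1). The number observed at a visit may differ.
- Half-width of the 95% interval = 1.96 × SD / √35 = 1.3, 2.0 or 2.7 mm.

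With SE = SD / √35 and no true change, the probability that the interval excludes zero is 1 − [Φ(1.96 − B/SE) − Φ(−1.96 − B/SE)]:

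| B (mm) | SD 4 | SD 6 | SD 8 |
|---|---|---|---|
| 0 | 5% | 5% | 5% |
| 0.5 | 12% | 8% | 7% |
| 1.0 | 32% | 17% | 12% |
| 2.0 | 84% | 51% | 32% |
| 3.0 | 99% | 84% | 60% |

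No formal test is planned, so these figures only show how easily the reported interval could come to suggest a rise in tear secretion. The effect may be nothing, or as large as the interval's half-width or larger.

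**4. Time cost of moving the wait.** Let t be the time taken by sensitivity testing. If the wait now comes first, photograph to strip takes 10 + t minutes; after the change it takes t + 10, so nothing is added. If testing now falls inside the wait, the time goes from 10 to t + 10, so t is added, at most 10 minutes. In both cases at least 10 minutes still separate the fluorescein photograph from the strip.

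**The case against.** A reader might infer that Schirmer is done immediately after the touch and that any recovery of sensation by itself raises the Schirmer change. The documents support neither statement. No section says that the strip follows at once. The wait is worded relative to Schirmer, so sensitivity may be tested inside it with minutes to spare. The Schedule order is only recommended, an explicit instruction to examine in order appears only at Visit 1 (which has no Schirmer), and the MOP may set an interval. Nor do the documents show that tearing from a filament touch lasts into a later strip test, or that the stimulus delivered stays constant as sensation changes. These points stand. They limit the claim to a possible carry-over of unknown size, but they do not supply the missing interval.

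Schirmer I is meant to include reflex tearing. Recovered sensation can raise it through the strip alone, with no prior touch. That is part of the measured construct, and moving the wait would rightly leave it in place. Only carry-over from the separate sensitivity test is at issue.

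The consequences are also limited. Schirmer is an exploratory objective, SAP Section 2.10 treats all efficacy analyses as exploratory, and an uncontrolled Schirmer change cannot be firmly attributed to treatment in any case. The primary variable, epithelial healing by staining grade at Week 8, is recorded before the touch. All of this stands and keeps the point minor.

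**Conclusion.** The point holds as a cheap improvement of minor severity. The listed order allows touch-evoked reflex tearing to carry over into Schirmer I at Visits 2, 4, 6 and 7. Because sensation is low at entry and expected to improve, any carry-over may grow after baseline and push the Schirmer change toward apparent benefit, and a single-arm design cannot correct for this afterwards.

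Confidence in the listed order is high; confidence in the size of the bias is low. The range of 0 to 3.0 mm rests wholly on assumed recovery shares and assumed wetting, and zero is a live possibility. The conclusion also assumes that the MOP does not already require an interval after aesthesiometry. It does not extend to the primary endpoint.

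**What to change.** In Protocol Sections 6.1.2, 6.1.4, 6.1.6 and 6.1.7, list the steps as: corneal photograph with fluorescein; corneal sensitivity; the existing 10-minute wait, timed from the last aesthesiometer touch; Schirmer I. Align the MOP, or, if it already sets an interval after the touch, state that interval in the protocol. The Schedule of Evaluations already has sensitivity before Schirmer and needs no reordering.

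Staining and photographs still come before any corneal contact, and sensitivity then follows the fluorescein photograph directly, as it does at Visit 1. If any patient has already had Visit 2 in the present order, keep that order for that patient so that the change from baseline compares like with like.

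The cost is an edit to four visit lists and the MOP. Visits lengthen by up to about 10 minutes where sites now test sensitivity during the wait, and not at all elsewhere. No procedure is added.
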